The aforementioned studies vary considerably in the quantity and composition of local anesthetic used intraoperatively, the location of injection, and in the administration of voiding trials postoperatively. Sample size of each study was also small and thus perhaps underpowered to detect statistically significant differences. Therefore, based on the limited existing data, we hypothesize that patients receiving retropubic normal saline compared to local anesthetic (e.g., lidocaine) will have a reduction in rates and duration of postoperative urinary retention following retropubic midurethral sling placement.

**Aim 1**: to compare the incidence of urinary retention following retropubic midurethral sling placement in those women receiving normal saline vs lidocaine for retropubic hydrodissection. We will compare rates of failed retrograde voiding trials between patients receiving normal saline and those receiving the same quantity of lidocaine. This will be completed using a standardized retrograde voiding trial 1-2 hours postoperatively (as outlined in "Data and Statistical Methods" below). We hypothesize that patients receiving normal saline will have a reduction in postoperative urinary retention following retropubic midurethral sling placement.

**Aim 2**: to assess postoperative pain in women receiving retropubic normal saline vs lidocaine during midurethral sling placement. Postoperatively, subjects will be asked to assess their pain using a VAS scale administered by nursing personnel at 2 hours (+/- 30 minutes) and again at 6 (+/- 30 minutes) hours following surgery, during the time of routine vital sign assessment. The subsequent pain assessments will be completed by the patient via an at-home form from discharge through postoperative day #7. Narcotic use will be queried through the electronic medical record as well as with a pain diary administered at time of discharge until postoperative day #7.

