Inclusion criteria includes the following: age 18 years or older, English speaking, and competent to give consent. Exclusion criteria includes a known intolerance or allergic reaction to local anesthetics, planned spinal anesthesia for the procedure, planned concomitant prolapse repair other than anterior repair, or preoperative voiding dysfunction as evidenced by a post-void residual (PVR) of 150 mL or greater. On average, our institution treats 60-80 patients per year with midurethral slings.

Informed consent will be obtained at the preoperative appointment. Demographic information including age, weight, height, body mass index (BMI), allergies, obstetrical, gynecological, medical, and surgical history will be collected from those subjects who agree to participate. Preoperative bladder testing obtained as part of routine clinical care will also be recorded,

Patients will be randomized in the preoperative area on the day of surgery to prevent randomization of patients who may go on to cancel or postpone surgery. Randomization will be created using a random numbers table with blocking into groups of 4. On the day of surgery, the operating room pharmacist will prepare 20 cc of either study drug, 0.5% lidocaine with epinephrine 1:200,000, or normal saline with epinephrine 1:200,000 in identical appearing 20cc syringes to be injected retropubically. Our group's routine clinical practice will inject the randomly assigned 20cc syringe retropubically along the path of the midurethral sling trocars. Suburethral injection of local anesthetic will be performed at surgeon discretion. Surgical teams, anesthesia teams and patients will be blinded to allocation assignment. The investigational drug pharmacist will maintain the randomization sequence.

Standard postoperative care will then be followed. Before discharge, as part of routine clinical care, all subjects will undergo a postoperative voiding trial as outlined below. A routine postoperative evaluation will be performed by the primary surgeon at a 6-week interval following surgery.

Table 1. Timeline of data collection

	Time of Data Collection/Eval						itions	
Data	Baseline	Intervention	Surgery	Pos	stoperative as			
				2 h	6 h	24h	Week 1	Week 6
				(+-30	(+- 30			
				mins)	mins)			
Retrograde Voiding Trial				Х				
VAS pain score	Х			Х	Х			
Narcotic requirements	Х		Х	Х	Х	Х	х	
Pain Diary						Х	х	
Demographic factors	Х							
Intraoperative factors			Х					
Side effects (APS-POQ-R)						Х		

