#### Postoperative pain

Visual Analog Scale (VAS) pain: Pain will be measured 2 hours (+/- 30 Minutes) and 6 hours (+/- 30 minutes) following surgery by VAS pain scales. VAS pain scales are unidimensional measures of pain intensity that are easily completed and scored. Subjects place an "X" on a 10-centimeter (cm) VAS line at the point that represents their pain intensity. The score is calculated by measuring the distance in millimeters (mm) along the 10 cm line where 0 represents "no pain" and 10 represents "worst pain." Scores range from 0-100mm. They have been widely used in diverse populations to assess pain. VAS pain scores will be used as the outcome measure in this study because they are easy to complete and because they are easily compared to prior studies. The 2-hour VAS score will be completed prior to discharge. The 6-hour VAS score will be returned via mail since patients are routine discharged a few hours after sling surgery.

Pain diary: Pain diaries will also be used in order to assess postoperative pain in the home setting. Pain diaries will be provided to all participants at time of discharge to be completed from POD #0 until postoperative day #7. Patients will be asked to register their pain intensity at home on a VAS scale once every morning and every evening. These will be returned by the patient via mail in self-addressed stamped envelopes.

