## **Data and Statistical Methods**

**Aim 1**: to compare the incidence of urinary retention following retropubic midurethral sling placement in those women receiving normal saline vs lidocaine for retropubic hydrodissection. Rates of postoperative urinary retention will be compared between groups using chi squared testing. Duration of urinary retention measured in days will be compared using t-tests or nonparametric testing as appropriate. To adjust for other factors that may impact voiding trial results, logistic regression analysis will be performed and will include variables identified as significant (p>0.01) on univariable analysis as well as intraoperative narcotic use, age, and estimated blood loss. All analyses will be performed using intention to treat. Data analyses will be done using SPSS and Matlab.

**Aim 2**: to assess postoperative pain in women receiving retropubic normal saline vs lidocaine during midurethral sling placement. VAS scores will be measured on a scale of 0-100mm with higher scores indicating worse pain. Change from baseline in VAS pain scores will be compared at each time point with t-tests. Narcotic requirements measured in morphine equivalent grams will be compared by t-tests (and

Wilcoxon rank-sum tests if non-parametric). Both VAS pain scores and narcotic requirements will be compared in an intention to treat analysis. Multivariable logistic regression analyses will be used to identify independent risk factors that predict pain at 2, 6 and 24 hours postoperatively. We plan to adjust for operating time, estimated blood loss, urinary retention, and concomitant procedures, as all of these may predict worse postoperative pain. Anything found to be different at baseline will also be included as covariates.

**Aim 3**: to assess patient satisfaction in women receiving retropubic normal saline vs lidocaine during midurethral sling placement. Patient satisfaction Likert scale questionnaires will be compared using t-tests with lower scores indicating worse satisfaction. T-tests (and Wilcoxon rank-sum tests if non-parametric) will be used to analyze results of individual APS-POQ-R questions.

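### Aim 2 compares arms by unadjusted t-tests on change in VAS although baseline VAS is scheduled and could be adjusted for at almost no cost; its logistic model for pain has no defined outcome

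*Combined protocol and SAP*

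**What the plan says.** Under Data and Statistical Methods, Aim 2, the arm comparison for pain is: "Change from baseline in VAS pain scores will be compared at each time point with t-tests". No covariate is named for it. Table 1 marks a VAS at baseline, 2 h and 6 h.

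The only adjusted pain analysis in the same paragraph is: "Multivariable logistic regression analyses will be used to identify independent risk factors that predict pain at 2, 6 and 24 hours postoperatively". Its covariates are then listed: "We plan to adjust for operating time, estimated blood loss, urinary retention, and concomitant procedures". The paragraph ends: "Anything found to be different at baseline will also be included as covariates".

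Under Postoperative pain the VAS is a length in millimetres: "Scores range from 0-100mm". The home diary is described there too: "Patients will be asked to register their pain intensity at home on a VAS scale once every morning and every evening". Table 1 marks the diary, but not the VAS row, at 24 h.

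**The concern.** There are two separate matters and one small one.

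**Arm comparison.** Subtracting baseline fixes the slope of follow-up on baseline at 1. If the true slope differs, the subtraction adds noise that regression would remove. The sentence on baseline differences does not repair this. It belongs to the risk-factor regression, and it brings in a covariate only when an imbalance happens to be seen.

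**Risk-factor model.** Logistic regression needs a binary or ordered response. Pain is a continuous length throughout, and no section says what counts as a pain event. Someone must supply that choice, possibly after seeing the data, and a reader could not tell a planned cut-off from a later one.

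**24 h value.** The diary is the evident source, but with two entries a day the plan does not say which one is the 24 h score.

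The section on potential risks names more pain without lidocaine as a risk of the saline arm. Any gain in voiding will therefore be weighed against pain, and a wider interval than the data require makes it harder to say how much extra pain can be ruled out.

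**Working it through.** **Inputs.** The plan gives no power, SD, correlation or target difference for VAS, so it has no figure of its own to reproduce here. From the Sample Size Calculation I take only n = 72 per group. All SDs, correlations and distributions below are assumptions.

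**Large-sample variances.** Set follow-up SD = 1. Let k = baseline SD / follow-up SD and r = the baseline to follow-up correlation.

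- Change score: 1 + k² − 2rk
- Baseline-adjusted regression (ANCOVA): 1 − r²
- Difference: k² − 2rk + r² = (k − r)², never negative, and zero only when r = k

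**Finite-sample cost.** Estimating one slope multiplies the ANCOVA variance by about 1 + 1/(2n − 4) = 1 + 1/140 = 1.007.

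**95% CI half-width.** This is t × SD × √variance × √(2/72), with t = 1.977, √(2/72) = 1/6 and an assumed follow-up SD of 25 mm. Example for k = 0.5, r = 0.1: change 1.977 × 25 × √1.15 / 6 = 8.83 mm; ANCOVA 1.977 × 25 × √(0.99 × 1.007) / 6 = 8.23 mm.

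| k | r | Change variance | ANCOVA variance | Ratio, large sample | Ratio, 72/arm | Half-width, change vs ANCOVA (mm) |
|---|---|---|---|---|---|---|
| 0.25 | 0.1 | 1.0125 | 0.99 | 1.023 | 1.015 | 8.29 vs 8.23 |
| 0.25 | 0.3 | 0.9125 | 0.91 | 1.003 | 0.996 | 7.87 vs 7.89 |
| 0.25 | 0.5 | 0.8125 | 0.75 | 1.083 | 1.076 | 7.42 vs 7.16 |
| 0.5 | 0.1 | 1.15 | 0.99 | 1.162 | 1.153 | 8.83 vs 8.23 |
| 0.5 | 0.3 | 0.95 | 0.91 | 1.044 | 1.037 | 8.03 vs 7.89 |
| 0.5 | 0.5 | 0.75 | 0.75 | 1.000 | 0.993 | 7.13 vs 7.16 |
| 1 | 0.3 | 1.40 | 0.91 | 1.538 | 1.528 | 9.75 vs 7.89 |
| 1 | 0.5 | 1.00 | 0.75 | 1.333 | 1.324 | 8.24 vs 7.16 |

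Half-widths scale with the assumed SD. At 15 mm, the gain over the six rows with k of 0.25 or 0.5 runs from −0.02 to 0.36 mm.

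**Skewed scores.** The ratio was simulated with 72 per arm, scores held within 0-100 mm, gamma-distributed follow-up and many zero baselines (4,000 trials per setting). It was 1.01 to 1.07 with k about 0.34, and 1.30 to 1.50 with k about 0.78.

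**Would the imbalance sentence help?** Suppose it did apply to the arm comparison and meant p < 0.05. In 20,000 simulated trials per setting, baseline VAS entered in about 5%. Variance relative to always adjusting was 1.39, against 1.53 for the plain change score, at k = 1 and r = 0.3. It was 1.11 against 1.15 at k = 0.5 and r = 0.1. Most of the loss remains.

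**Cost of a cut-off.** For a normal score and small effects, a cut at quantile p keeps φ(z_p)² / [p(1 − p)] of the information: 0.637 at the median, 0.490 at a 20/80 split and 0.342 at 10/90.

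**Urinary retention as a covariate.** Retention is the trial's primary outcome, so adjusting for it may remove part of any arm effect on pain. Timing is a further problem. The voiding trial is done at 1-2 h with up to 1 h to void, so the result may come as late as 3 h after surgery. The 2 h VAS window is 1.5 to 2.5 h.

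**The case against.** The strongest reply is that the arm comparison is a choice between two valid methods for a secondary outcome. The t-test is unbiased. Patients having incontinence surgery plausibly have low, narrowly spread baseline pain, so the rows with k of 0.25 or 0.5 may be the realistic ones. There the half-width changes by −0.03 to 0.61 mm at an SD of 25 mm, and in two of the six rows adjusting is very slightly worse. The large gains need equal SDs.

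This stands as a limit on size: the benefit may be close to nil. It does not favour the t-test. With SDs and correlation unknown, one method risks under 1% of variance in these settings and the other may carry over 50% more.

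Three smaller points are also fair. The imbalance calculation assumes a p < 0.05 reading that the plan does not state. The information figures assume a normal score. And the plan does not say that arm is in the risk-factor model, so the warning about retention matters only if arm is included; the timing problem at 2 h remains either way.

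None of this touches the undefined logistic outcome, which depends on no assumed SD.

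**Conclusion.** The concern holds, and the plan should be changed. The change-score t-test is valid but in large samples never more precise than adjusting for the scheduled baseline VAS. Its excess variance runs from nil to about 16% when baseline SD is a quarter to a half of follow-up SD, and is 33% to 54% with equal SDs, for the correlations tabulated. All of these rest on assumed SDs and correlations, and the smaller figures may be the more realistic. The possible loss from adjusting is about 0.7% at most in these settings.

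The logistic model cannot be run as written, because no pain event, cut-off or ordinal form is defined. That conclusion needs no numerical assumption. The unnamed 24 h diary entry is a minor gap.

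**What to change.** 1. **Arm comparison.** At each time point, regress postoperative VAS in mm on arm and baseline VAS in all cases, whether or not an imbalance is seen. Report the adjusted mean difference with its 95% CI. To cover skewness, name one sensitivity analysis now and always report it: a bootstrap 95% CI for the same difference, resampling within arm.
2. **Risk-factor model.** Use linear regression on VAS in mm with the listed covariates plus baseline VAS. If odds ratios are wanted, fix the cut-off or an ordinal model before unblinding. Do not read an arm effect from this model, because retention is a covariate. Either leave retention out of the 2 h model or state how its timing is handled.
3. **24 h value.** Name the diary entry, for example the postoperative day 1 entry nearest 24 h after surgery.

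The cost is wording only, since baseline VAS is already scheduled and both analyses are kept. Risk-factor results would be in mm rather than odds ratios. A rule for a missing baseline VAS is needed; the overall baseline mean, computed without regard to arm, would do.

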#### Narcotic requirements

Morphine equivalents: Doses of narcotic pain medications administered to subjects during the intra- and postoperative period will be abstracted from the EMR. Narcotics will be converted to morphine equivalents, in grams, using an equianalgesic dosage table. Narcotic use following hospital discharge will be measured by a 7-day diary, which will also be converted to morphine equivalents. Morphine equivalents have been widely used in the study of postoperative pain.

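### Baseline narcotic requirement is scheduled but unused in the Aim 2 narcotic comparison, so habitual opioid intake stays in the outcome and costs precision

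*Combined protocol and SAP*

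**What the plan says.** **Eligibility.** Under Study Entry and Recruitment, the criteria begin "Exclusion criteria includes a known intolerance or allergic reaction to local anesthetics, planned spinal anesthesia for the procedure" and go on to other planned prolapse repair and a raised post-void residual. Potential Risks, Issues, and Solutions adds severe dementia. None of these concerns current opioid use or chronic pain.

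**Outcome.** The Narcotic requirements section states "Doses of narcotic pain medications administered to subjects during the intra- and postoperative period will be abstracted from the EMR" and "Narcotic use following hospital discharge will be measured by a 7-day diary, which will also be converted to morphine equivalents". It does not separate intake that predates surgery from new use.

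**Baseline.** In Table 1 the row "Narcotic requirements" is marked at Baseline, Surgery, 2 h, 6 h, 24 h and Week 1. No section says how the baseline value is obtained or which analysis uses it.

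**Analysis.** Data and Statistical Methods, Aim 2: "Narcotic requirements measured in morphine equivalent grams will be compared by t-tests (and", the bracket continuing "Wilcoxon rank-sum tests if non-parametric". No baseline term appears. The sentence before it treats pain differently: "Change from baseline in VAS pain scores will be compared at each time point with t-tests". The only Aim 2 models are for pain: "Multivariable logistic regression analyses will be used to identify independent risk factors that predict pain at 2, 6 and 24 hours postoperatively". A rule at the end of that paragraph adds covariates for baseline factors on which a difference has been found.

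**The concern.** A woman on daily opioids will usually go on taking them after the sling. Her ordinary intake then forms part of her postoperative total, alongside whatever the operation and the allocated injection added. The plan recognises the need for a baseline reference for one Aim 2 outcome (VAS) and omits it for the other, although the value is due to be collected.

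Potential Risks, Issues, and Solutions names greater pain without lidocaine as a risk of the placebo arm, and narcotic use is one of the measures that would show such a cost. If habitual intake adds enough noise to hide a real increase, a null result could be read as reassurance that leaving out lidocaine costs patients nothing.

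**Working it through.** **1. The plan's own figure.** The only sample size concerns voiding-trial failure: 35% against 15%, two-sided 0.05, 80% power, 72 per group. The pooled formula gives n = [1.960·√(2·0.25·0.75) + 0.842·√(0.35·0.65 + 0.15·0.85)]² / 0.20² = (1.200 + 0.501)² / 0.04 ≈ 72.4, or 73 rounded up. The stated figure is reproduced to within one woman. It does not bear on narcotic use, for which the documents give no standard deviation, target difference or number of prior users. Everything below uses assumed inputs.

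**2. Assumptions for steps 3 to 5.** 72 women per arm. Seven-day use in women without prior opioids has mean 40 mg and SD 40 mg morphine equivalents. The true ratio between arms is 1.5, a difference of 20 mg. Prior users take 30 to 60 mg a day, or 210 to 420 mg over 7 days, in addition to surgical need.

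**3. Chance imbalance.** One extra prior user in an arm moves its mean by 210/72 = 2.9 mg to 420/72 = 5.8 mg. Three extra users move it by 8.8 to 17.5 mg, against an assumed true difference of 20 mg.

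**4. Spread.** With a fraction f of users taking b mg over 7 days, SD = √(40² + f(1−f)b²). For f = 2% (0.02 × 144 = 2.9, about 3 women in the trial):
- b = 210: √(1600 + 864) = 49.6 mg
- b = 420: √(1600 + 3457) = 71.1 mg

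Normal-approximation power for a 20 mg difference falls from 85% (SD 40) to 68% and 39%.

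**5. Simulation.** 2,000 trials per setting, with lognormal use in non-users and habitual intake continuing at about the baseline level, recorded with some error. Power with no users is lower than in step 4 because the ratio of 1.5 also scales the SD of the higher arm. In each cell the first figure is for 30 mg a day and the second for 60.

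| Prior users | t-test, raw total | Rank-sum, raw total | Linear model with baseline |
|---|---|---|---|
| 0% | 68-70% | 81% | 68-70% |
| 2% | 54%, 38% | 78%, 76% | 69%, 66% |
| 5% | 40%, 21% | 72%, 73% | 66%, 64% |
| 10% | 30%, 13% | 66%, 62% | 67%, 58% |

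With no true effect, every method rejects in 3.8 to 5.2% of trials.

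**6. Could a few users create a significant difference?** Second set of assumptions: 75 per arm, non-users with mean 30 and SD 30 mg, no true effect, and three users all in one arm (p = 3/75 = 0.04).
- m = 210: mean 0.96·30 + 0.04·210 = 37.2, SD √(900 + 0.04·0.96·180²) = 46.3, z = 7.2 / √(46.3²/75 + 30²/75) = 1.13, P about 0.26
- m = 420: mean 45.6, SD 82.1, z = 15.6 / √(82.1²/75 + 30²/75) = 1.55, P about 0.12
- Without limit on the dose: z tends to 0.04 / √(0.04·0.96/75) = 1.77

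The users raise the SD together with the mean, so the expected z stays below 1.96. All three fall in the same arm only about 2 × (1/2)³ = 1/4 of the time.

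**The case against.** Four points can be made for the plan.

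**The rank-sum alternative.** Narcotic totals with a few very large values are what it is for, and with 2% users it loses only about 3 to 5 points. This largely stands. A reader might infer that a handful of habitual users would overwhelm the comparison whichever test is used; the plan's own alternative rules that out. But the plan names the t-test first and gives no criterion for switching. Ranks also leave habitual intake in the outcome, and their power falls to 66-62% at 10% users.

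**Randomisation and blinding.** Habitual intake is expected equally in both arms, so it cancels on average. This stands in full. A reader might infer systematic bias, or a false positive produced by uneven allocation. Steps 5 and 6 support neither: the type I error stays near 5%, and three users in one arm do not bring the expected z to significance.

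**The baseline-covariate rule in Aim 2.** It might seem to bring baseline narcotic use into the analysis. It does not cover this outcome. It closes the description of the pain regressions, it applies only when a difference is found, and no regression of narcotic use is planned. Users split evenly between arms would add variance without triggering it.

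**Whether such women enrol.** The documents do not say. This stands, and it makes the size conditional on assumptions, but it does not explain why a scheduled baseline value has no use.

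**Conclusion.** The gap is real. Women with existing opioid use are eligible, their baseline requirement is scheduled, and the planned narcotic comparison does not use it. The consequence is lost precision and an estimate that chance imbalance can move, without systematic bias or inflated type I error.

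Under the assumed inputs the loss is large for the t-test even at 2% users (68-70% down to 54-38%) and modest for the rank-sum test while users are few (81% down to 78-76%). These figures depend on assumed prevalence, dose, spread and effect, and on habitual intake continuing after surgery; none comes from the documents. The effect is confined to one secondary outcome. The primary chi-squared comparison and its sample size are unaffected, and VAS already has a baseline reference.

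**What to change.** In Data and Statistical Methods, Aim 2:

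1. Prespecify the between-arm comparison of narcotic use as a regression with baseline narcotic requirement as a covariate, fitted on ranks if the totals are skewed, and state how skewness will be judged. The rank form matters: in the table above, the linear adjusted model does no better than the plain rank-sum test when users are few.
2. Define the baseline value as daily morphine equivalents, with its source and a default when it is missing. The Narcotic requirements section currently covers only perioperative doses and the diary.
3. Add a sensitivity analysis restricted to women with zero baseline use.

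Eligibility and visits do not change. The cost is slightly more analysis work and a rule for missing baseline values. A rank regression does not give a difference in milligrams, so arm medians should be reported beside it.

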# **Sample Size Calculation**

The rate of postoperative urinary retention following midurethral sling at our institution is 35% (data unpublished). To detect a clinically significant reduction of postoperative urinary retention of 20%, 72 subjects per group would be needed to provide 80% power with a two-sided alpha of 0.05. After adjusting for a 5% loss to follow-up rate, 75 subjects per arm would be required.

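### In the secondary Aim 2 pain model, baseline variables enter only if the arms happen to differ on them, so chance, not relation to pain, selects them

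*Combined protocol and SAP*

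**What the plan says.** All of this is in the combined protocol and SAP.

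- **Main Aim 2 comparison** (Data and Statistical Methods): "Change from baseline in VAS pain scores will be compared at each time point with t-tests". Narcotic use is compared by t-test or Wilcoxon test. Neither comparison uses covariates.
- **Adjusted model** (same section): "Multivariable logistic regression analyses will be used to identify independent risk factors that predict pain at 2, 6 and 24 hours postoperatively".
- **Fixed covariates** (same section): "We plan to adjust for operating time, estimated blood loss, urinary retention, and concomitant procedures, as all of these may predict worse postoperative pain".
- **Added covariates** (next sentence): "Anything found to be different at baseline will also be included as covariates". No candidate list, test, threshold, cap or required link with pain is given, and no other section narrows the rule.
- **Allocation** (Study Entry and Recruitment): "Randomization will be created using a random numbers table with blocking into groups of 4".
- **Variables available** (same section): "Demographic information including age, weight, height, body mass index (BMI), allergies, obstetrical, gynecological, medical, and surgical history will be collected". Preoperative bladder testing is also recorded, and Table 1 schedules VAS and narcotic requirements at baseline.

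**The concern.** In a randomised comparison, a baseline difference between arms says nothing about whether the variable predicts pain. A covariate earns its place by its relation to the outcome, and a strong predictor is worth including even when the arms are perfectly balanced on it. The rule reverses this: a strong predictor is left out of most possible trials, and an irrelevant variable enters just as often.

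No demographic, history or preoperative pain variable is named for this model. Imbalance is therefore the only stated route by which age, BMI, surgical history, baseline VAS or baseline narcotic use can enter it.

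Two things are at stake: the precision that adjustment should bring, and a model settled before the arms are compared. Because the plan does not define what counts as different, the choice can also be made after the data are seen. Increased pain without lidocaine is a risk that the protocol itself lists for the saline arm, so the pain model should be fixed in advance.

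**Working it through.** **Inputs from the documents.** The Sample Size Calculation section states that "72 subjects per group would be needed to provide 80% power with a two-sided alpha of 0.05", from a 35% retention rate and a 20-point reduction. The point disputes no stated figure; 72 per arm is only the size used in the illustration. Check with the pooled two-proportion formula, mean proportion 0.25:

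n = [1.96·√(2·0.25·0.75) + 0.842·√(0.35·0.65 + 0.15·0.85)]² / 0.20² = (1.200 + 0.501)² / 0.04 ≈ 72.4, which reproduces 72 (73 if rounded up).

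**Assumptions, not in the documents.** A screen at p<0.05; independent baseline variables; a pain effect of 0.4 SD; the correlation r of one baseline variable with pain; a linear model in place of the logistic one.

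**Step 1: number of candidates.** The enrolment list names 9 items or groups of items. Bladder testing, baseline VAS and baseline narcotic use make 12. Splitting the history groups could give 15.

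**Step 2: chance that at least one enters.** With k variables this is 1 − 0.95^k.

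| k | At p<0.05 |
|---|---|
| 5 | 23% |
| 9 | 37% |
| 12 | 46% |
| 15 | 54% |
| 20 | 64% |

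With a p<0.10 screen and 12 variables it is 72%. The expected number added from 12 is 12 × 0.05 = 0.6, or 1.2 at p<0.10.

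**Step 3: power by formula.** With 72 per arm, power ≈ Φ(d·√(72/2) − 1.96). Adjusting for one predictor raises the effective d from 0.4 to 0.4/√(1 − r²).

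- No adjustment: Φ(0.400 × 6 − 1.96) = Φ(0.44) ≈ 67%
- r = 0.3: d = 0.419, Φ(0.56) ≈ 71%
- r = 0.5: d = 0.462, Φ(0.81) ≈ 79%

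**Step 4: the rule by simulation.** 72 per arm, 12 independent baseline variables of which one is prognostic, 6,000 runs per setting.

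| r | Power, unadjusted | Power, rule | Power, predictor prespecified | Type I error, rule | Prognostic variable selected (0.4 SD runs) |
|---|---|---|---|---|---|
| 0.3 | 66.9% | 66.0% | 70.5% | 4.8% | 5.3% |
| 0.5 | 65.3% | 65.7% | 77.6% | 4.6% | 5.2% |
| 0.7 | 65.6% | 66.8% | 91.1% | 3.6% | 5.2% |

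The simulation error of a power figure is about √(0.66 × 0.34 / 6,000) = 0.6 points, so the rule and no adjustment cannot be told apart in any practical sense. At r = 0.5 and a 0.4 SD effect, the standard deviation of the estimated effect is 0.168 unadjusted, 0.163 under the rule and 0.144 with the predictor prespecified. Between 170 and 198 different covariate sets arose in each 6,000-run setting, even with a fixed threshold.

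With 15 variables, power under the rule was 65-68%, against 69% (r = 0.3), 79% (0.5) and 84% (0.6) with the predictor prespecified. Type I error under the rule was about 4-4.5%.

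**The case against.** The strongest reply concerns scope, and most of it stands.

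- **The model is not wholly open.** A reader might infer that the plan picks imbalances in place of predictors of pain, or that the whole model is unknown. The documents do not support that: four covariates are fixed in advance because they may predict pain. What is open is which baseline variables join them.
- **The main tests are untouched.** A reader might infer that the trial's pain comparison or primary result is at risk. The rule feeds only a secondary logistic model meant to find risk factors. The Aim 2 t-tests and Wilcoxon tests and the primary chi-squared test do not use it.
- **False positives are not inflated.** Applied mechanically, the rule is slightly conservative. The undefined criterion does leave room for choice, but nothing in the documents shows that this room would be used, and its effect cannot be calculated.
- **The power gain is assumed.** The documents give no correlation of any baseline variable with pain. With weak predictors, prespecified adjustment gives about 66% (r = 0.1) or 68% (r = 0.2), against 66-67% unadjusted. The simulations are linear and omit the four fixed covariates, so the figures show direction and rough size only.
- **Independence is assumed.** Weight, height and BMI are plainly related, so the chance that at least one variable enters is approximate.

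The four fixed covariates do not remove the point. Operating time, blood loss and urinary retention are observed after randomisation, and none of the four is a measure of preoperative pain or analgesic use. Whether post-randomisation variables belong in this model is a separate question.

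**Conclusion.** The point holds for the secondary Aim 2 logistic model and no further. Its rule for baseline variables selects on chance, leaves that part of the model undetermined until the arms are compared, and gives essentially no gain in precision. The text does not say that the difference is between arms, but that is the natural reading in a two-arm trial.

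Under the stated assumptions, there is a 37-54% chance that at least one of 9-15 variables enters by chance. Power stays at about 66%, as without adjustment, where one prespecified predictor would give about 69-70% at a correlation of 0.3 and 78% at 0.5. Type I error is about 4-4.5% instead of 5%. The gain forgone is small if the available predictors are weak. The threshold, the variable count, the correlations, the 0.4 SD effect and the linear model are all assumptions. This is a cheap improvement, not a threat to the trial's main conclusions.

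**What to change.** Delete the sentence. In its place, name the baseline covariates for the Aim 2 model now, from data already scheduled for collection: first baseline VAS and baseline narcotic use (Table 1), with age and BMI if wanted. Include them whether or not the arms differ. Report the baseline table descriptively, without significance tests between arms.

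The cost is one sentence in Data and Statistical Methods, with no new data and no additional patients. The only loss is that adjustment for an observed imbalance moves to a sensitivity analysis labelled as such.
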